3.5. Baseline Variables

Percent weight loss in the 6 months prior to screening visit (SV) will be calculated as:

weight from 6 months prior to SV [kg] — SV weight [kg]

weight from 6 months prior to SV [kg]

PFIZER CONFIDENTIAL

DMB02-GSOP-RF02 8.0 Statistical Analysis Plan Template

TMF Doc ID: 98.03

Page 23 of 60

If weight from 6 months prior to SV is missing, weight from the closest timepoint after 6 months should be used, e.g. if a participant has a weight available from 8 months, 6 months, and 4 months prior to SV, the weight from 6 months prior to SV should be used. If a participant has a weight available for 9 months, 4 months, and 2 months prior to SV, the weight from 4 months prior to SV should be used.

BMI-adjusted weight loss category (0/1/2/3/4) will be determined based on the percent weight loss in the 6 months prior to screening visit and the BMI at screening using the following grading system developed by Martin (2015)¹:

BMI (kg/m²) 25 22 0 3 2.5 Weight Loss (%) 2 2 2 3 6 3 3 3 4 11 3 3 3 4 4 15 3 4 4 4

Sarcopenia status at baseline will be determined. Participants with baseline lumbar skeletal muscle index (LSMI) $\leq 38.5 \text{ cm}^2/\text{m}^2$ in women, and $\leq 52.4 \text{ cm}^2/\text{m}^2$ in men, will be defined as having sarcopenia.

The following baseline inflammation variables will be determined for participants, if possible (note that the recorded units may differ from the units required in calculations):

- C-reactive protein (CRP) (mg/dL): from Retained Research Samples on Day 1
- CRP-albumin ratio: CRP on Day 1 (mg/dL) / albumin (mg/dL) on Day 1

[Note: CRP concentrations below the limit of quantification (BLQ) will be set to the lower limit of quantification (LLQ) prior to calculation of the ratio]

Modified Glasgow Prognostic Score on Day 1:

0: if CRP ≤ 1 mg/dL 1: if CRP > 1 mg/dL 2: if CRP > 1 mg/dL and albumin < 3.5 g/dL

- Neutrophil-lymphocyte ratio (NLR): neutrophil count at screening / lymphocyte count at screening
- Platelet-lymphocyte ratio (PLR): platelet count at screening / lymphocyte count at screening

4. ANALYSIS SETS (POPULATIONS FOR ANALYSIS)

Data for all participants will be assessed to determine if participants meet the criteria for inclusion in each analysis population prior to unblinding and releasing the database and classifications will be documented per standard operating procedures.

Participant Analysis Set	Description
Enrolled	"Enrolled" means a participant's, or their legally authorized representative's, agreement to participate in a clinical study following completion of the informed consent process and randomization to study intervention. A participant will be considered enrolled if the informed consent is not withdrawn prior to participating in any study activity after Screening. Potential participants who are screened for the purpose of determining eligibility for the study, but do not participate in the study, are not considered enrolled, unless otherwise specified by the protocol.
Evaluable	All participants randomly assigned to study intervention and who take at least 1 dose of study intervention. Participants will be analyzed according to the randomized intervention.
Safety analysis set	All participants randomly assigned to study intervention and who take at least 1 dose of study intervention. Participants will be analyzed according to the study intervention they actually received. This will be the study intervention received by the participant for the majority of the timepoints during the relevant part of the study. If a participant receives an equal number of different doses, then the lowest of those doses will be used. If a participant receives an equal number of placebo and a given dose of ponsegromab, the ponsegromab dose will be used.

Defined Analysis Set	Description
Censored	All evaluable participants. For participants who discontinue study intervention, or receive a prohibited procedure or prohibited medication, all observations post-discontinuation, or post-procedure, will be censored and treated as missing data. For participants who miss a dose, or receive an incomplete dose, all observations post-missed/incomplete dose will be censored and treated as missing data.
Complete	All evaluable participants. For participants who discontinue study intervention, receive a prohibited procedure or prohibited medication, and/or miss a dose,

Defined Analysis Set	Description
	or receive an incomplete dose, all observations post- discontinuation, post-procedure or post- missed/incomplete dose will be included in the analysis set.
PK	All participants randomly assigned to study intervention and who take at least 1 dose of ponsegromab and in whom at least 1 PK concentration value is reported.
PD	All participants randomly assigned to study intervention and who take at least 1 dose of study intervention and in whom at least 1 PD (GDF-15) concentration value is reported.
Immunogenicity	All participants randomly assigned to study intervention and who take at least 1 dose of ponsegromab and in whom at least 1 ADA result is reported.

For participants who discontinue study intervention, the date of discontinuation of study intervention is defined as the date of last dose of IP + 29 days.

Listings of non-drug treatment(s)/procedure(s) and concomitant medication(s) will be provided (see Section 6.6.3). These will be blinded tables and will be reviewed prior to database lock to determine which procedures and medications would be classed as "prohibited".

Participants who are randomized to the wrong stratum, in error, will have the incorrect stratum assignment remain in IMPALA but the clinical database will include the correct stratum. The latter will subsequently be used for all relevant analyses, as appropriate.

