## 1.2. Schema

#### 1.3. Schedule of Activities

The SoA table provides an overview of the protocol visits and procedures. Refer to the section of the protocol for detailed information on each procedure and assessment required for compliance with the protocol.

The investigator may schedule visits (unplanned visits) in addition to those listed in the SoA table, to conduct evaluations or assessments required to protect the well-being of the participant.

Table 1.	Schedule of Activities for Part A Double-Blind
----------	--

Visit Identifier	Screening				]	Part A: D	ouble-Bl	ind a		F/U Part A	ED Part A
Abbreviations used in this table may be found in											
Appendix 13											
Week #			4	5 b,c	8 d	9 c,e (PK substudy only)	10 c,f	11 c,e (PK substudy only)	12	16	
Day -relative to start of study intervention (Day 1)	-28 to -7	1	29	36	57	64	71	78	85	113	
Visit Window (Days)			±3	-3/+7	±3	±2	±7/±3 f	±2	±2	+7	
Informed consent	X										
Review eligibility criteria	Х	Х									
Medical History and Physical Examination											
Medical history	X										
Demography	X										
Full Physical examination (+ Height at Screening only) g	X								Х		Х
Abbreviated Physical examination g			Х		Х						
Vital signs	X		Х		Х				Х		Х
12-Lead ECG	Х				Х				Х		Х
ECOG PS	X								Х		Х
Contraception check	Х	Х	Х		Х				Х	Х	Х
Laboratory Assessments											
Hematology	X				Х				Х		Х
Blood chemistry	X				Х				Х		Х
Pregnancy test h	Х	Х	Х		Х				Х	Х	Х
Blood sample for GDF-15 (Roche Assay)	X										
Blood sample for GDF-15 (Pfizer Assay(s)) i	X	Х	X	Х	Х	Х	X	Х	Х	Х	Х
Blood sample for ponsegromab PK i		Х	Х	Х	Х	Х	X	Х	Х	Х	Х

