# 7. DISCONTINUATION OF STUDY INTERVENTION AND PARTICIPANT DISCONTINUATION/WITHDRAWAL

#### 7.1. Discontinuation of Study Intervention

It may be necessary for a participant to permanently discontinue study intervention. Reasons for permanent discontinuation of study intervention may include the following:

- Progression of underlying disease such that the investigator no longer considers participation appropriate, or of potential benefit to the participant.
- Hospitalization that in the opinion of the investigator would render continued participation unfeasible.
- If a participant experiences Grade 3 AEs judged by the Investigator as related to randomized study intervention, the study intervention will be temporarily discontinued until the treatment-related AEs return to Grade 2 (or less). If the treatment-related AEs return to Grade 2 (or less) or resolve within 4 weeks, continuation of dosing with study intervention may be considered. If these AEs do not return to Grade 2 (or less) within 4 weeks, and after discussion with the sponsor, the participant will be permanently discontinued from the study intervention.

- If a participant experiences Grade 4 AEs judged by the Investigator as related to randomized study intervention, the participant will be permanently discontinued from the study intervention.
- Severe allergic reaction to study intervention.
- Intent to become pregnant or pregnancy confirmed by b-hCG testing.
- Drug-induced liver injury as described in Section 10.6, Appendix 6.

Note that discontinuation of study intervention does not represent withdrawal from the study. If study intervention is permanently discontinued, the participant should remain in the study to be evaluated for follow up. All cases of planned or potential discontinuation of study intervention should be discussed with Sponsor before classifying a subject as 'Discontinued from Study Intervention' and completing an Early Termination visit. See the SoA for data to be collected at the time of discontinuation of study intervention and follow-up for any further evaluations that need to be completed.

In the event of discontinuation of study intervention, it must be documented on the appropriate CRF/in the medical records whether the participant is discontinuing further receipt of study intervention or also from study procedures, posttreatment study follow-up, and/or future collection of additional information.**Follow-Up:** 

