2.2.1. Primary Estimand(s)

Estimands related to the body weight primary objective:

Estimand 1 (similar to "hypothetical") is intended to provide a population level estimate of the treatment effect on the change from baseline in body weight for ponsegromab compared with placebo in all evaluable participants under the scenario of no discontinuation of study intervention and without the potential confounding effect of prohibited procedures, prohibited medications or participants' non-compliance with dosing (ie, using the Censored analysis set, as defined in Section 4).

 Population: Participants with cancer, cachexia, and elevated concentrations of GDF-15.

- Endpoint: Change from baseline in body weight at Week 12.
- Intercurrent Events:
 - Discontinuation of study intervention: Data collected after a participant has discontinued study intervention will be censored and treated as missing data.
 - b. Prohibited procedures: Data collected after a participant has undergone prohibited procedures, that would modulate the primary endpoint, will be censored and treated as missing data. Any procedures will be reviewed prior to database lock to determine which would be classed as "prohibited" for this estimand.
 - c. Prohibited medications Data collected after a participant has received prohibited medications, that would modulate the primary endpoint, will be censored and treated as missing data. The list of concomitant medications will be reviewed prior to database lock to determine which would be classed as "prohibited" for this estimand.
 - d. Inadequate compliance: Data collected after a participant has missed a dose, or has received an incomplete dose, will be censored and treated as missing data.
 - Missing data due to censoring, study withdrawal or other reasons, are assumed to be missing at random in the analysis.
- Population-level summary: Difference in mean change from baseline body weight at Week 12 between ponsegromab and placebo.

Estimand 1b (similar to "treatment policy") is intended to provide a population level estimate of the treatment effect on the change from baseline in body weight for ponsegromab compared with placebo in all evaluable participants regardless of discontinuation of study intervention, dosing compliance, prohibited procedures or prohibited medications (ie, using the Complete analysis set as defined in Section 4).

- Population: Participants with cancer, cachexia, and elevated concentrations of GDF-15.

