6.1.1.1. Main Analysis

Absolute values, changes from baseline and percent changes from baseline in body weight will be summarized descriptively by treatment group and timepoint, as described in Section 5.2.1. Tables will include baseline and all post-baseline timepoints. Box and whisker plots (or similar) of absolute values, changes from baseline and percent changes from baseline over time will also be produced, with all treatments on the same plot.

Change from baseline in body weight will be analyzed using an MMRM model as described in Section 5.2.3. All post-treatment dosing timepoints up to Week 12 (ie. Weeks 4, 8 and 12) will be included in the model. Additional terms for type of therapy [i.e. platinum or not] and type of cancer will be fitted in the model. Additional plots of LS means and differences (including 90% CIs for both), for Week 12 only, will be produced over treatment.

A Bayesian E_{max} model, as described in Section 5.2.4, will then be fitted to the Week 12 LSmeans and SEs from the MMRM analysis. This will be used to estimate the treatment effect related to the primary Estimand 1 (as described in Section 2.2.1). If the E_{max} model analysis is not performed, the primary results for the study will be based on the MMRM results at Week 12.

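### The last dose + 29 days cut-off in SAP section 4 drops late but in-window Week 4 and Week 8 weights in participants who discontinue, and keeps the same weights in those who continue

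*SAP*

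**What the plan says.** SAP section 4 fixes a date for participants who stop study intervention: "the date of discontinuation of study intervention is defined as the date of last dose of IP + 29 days". It gives no such clock for participants who continue.

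The date matters because of Estimand 1 (SAP 2.2.1): "Data collected after a participant has discontinued study intervention will be censored and treated as missing data". The Censored set in SAP section 4 repeats this: "all observations post-discontinuation, or post-procedure, will be censored and treated as missing data". SAP section 6 makes that set the default for all analyses, and SAP 6.1.1.1 applies it to the primary MMRM: "All post-treatment dosing timepoints up to Week 12 (ie. Weeks 4, 8 and 12) will be included in the model". The Week 12 LS means and standard errors from that model then go into the Bayesian Emax model.

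Protocol 1.3, Table 1, puts the Part A doses on Days 1, 29 and 57 and the modelled weights on Days 29, 57 and 85. The windows are ±3 days at Weeks 4 and 8 and ±2 days at Week 12.

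Weights after the last dose can exist, because Protocol 7.1 states: "If study intervention is permanently discontinued, the participant should remain in the study to be evaluated for follow up".

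**The concern.** The cut-off is one day longer than the nominal 28-day interval and makes no allowance for the visit windows. Take two participants dosed on Day 1 and weighed on Day 32. Both visits are in window and the time since dosing is the same. The plan keeps the weight of the one who goes on to dose 2 and deletes the weight of the one who stops. What differs is a status acquired after randomization, not the measurement.

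A participant who stops after dose 1 and is weighed on Day 31 or 32 loses the only modelled post-baseline weight and so contributes nothing to the MMRM. Someone who stops after dose 2 can lose the Week 8 value in the same way. The model then relies on missing at random where an in-window observation was available.

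**Working it through.** **Inputs.** Cut-off: last dose + 29 days (SAP 4). Nominal days and windows: Protocol 1.3, Table 1. Planned size 168 and discontinuation rate about 30%: Protocol 9.5.

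**The plan's own figures.** Nominal gaps are 29 − 1 = 28, 57 − 29 = 28 and 85 − 57 = 28 days, so a participant seen exactly on schedule is never affected. For the discontinuation rate, 168 × 0.70 = 117.6 completers, which agrees with the plan's approximate 120, and 168 × 0.30 = 50.4 discontinuers.

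**In-window gaps.** Gap = visit day − day of last dose; a weight is censored in a discontinuer when the gap exceeds 29.

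| Interval | Dose days | Visit days | Gap range | Combinations with gap > 29 |
|---|---|---|---|---|
| Dose 1 to Week 4 | 1 | 26–32 | 25–31 | 2 of 7 (28.6%) |
| Dose 2 to Week 8 | 26–32 | 54–60 | 22–34 | 15 of 49 (30.6%) |
| Dose 3 to Week 12 | 54–60 | 83–87 | 23–33 | 10 of 35 (28.6%) |

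In the first row the affected days are 31 and 32. In the second, the visit offset must exceed the dose offset by 2 to 6 days: 5 + 4 + 3 + 2 + 1 = 15 pairs. In the third, dose offsets −3, −2, −1 and 0 give 4 + 3 + 2 + 1 = 10 pairs. If *after* were read as *on or after*, gaps of 29 days would go too, and the share would be 43% in every row (3/7, 21/49, 15/35).

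**Sensitivity to where visits fall.** The percentages above treat all in-window days as equally likely, which is an assumption. With triangular weights peaking at the nominal day (1, 2, 3, 4, 3, 2, 1), Week 4 gives (2 + 1)/16 = 18.75% and Week 8 gives 66/256 = 25.8%.

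**Count at Weeks 4 and 8.** The documents do not say when discontinuers stop. Assume an even split over the three doses: 50.4 × 2/3 = 33.6 stop after dose 1 or dose 2, or 16.8 after each.

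- Uniform days, all attend the closing visit: 16.8 × 0.286 + 16.8 × 0.306 = 4.8 + 5.1 ≈ 10 weights.
- Triangular days, all attend: 16.8 × 0.1875 + 16.8 × 0.258 = 3.2 + 4.3 ≈ 7.5 weights.
- Half attend: about 5 and about 4 weights respectively.

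Ten weights are 10/504 = 2% of all scheduled modelled weights (168 × 3), or 10/336 = 3% of those at Weeks 4 and 8. The count scales with the assumed number who stop after dose 1 or 2.

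**The case against.** The best defence is that, under an estimand that supposes no discontinuation, 29 days covers the whole dosing interval plus a day, and some cut-off is needed. The rule is the same in every arm, and participants are classified before unblinding. Among discontinuers, whether a weight is lost depends on the visit date, not on the weight itself. Estimand 1b repeats the body-weight analysis on the Complete set and keeps all these values.

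Much of that stands as to size. It does not remove the inconsistency. The plan already accepts gaps of 30 to 34 days as on treatment for everyone who continues, so 29 days is not a limit on exposure that it applies generally. Estimand 1b is labelled exploratory and answers a different question, because it also restores all the data that Estimand 1 means to exclude.

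Three stronger readings are tempting, and the documents do not support them.

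- *Week 12 values are lost.* A participant dosed on Day 54 and weighed on Day 85 has a 31-day gap, and a third of 50 discontinuers at 28.6% would be about 5 Week 12 weights. That person has had all three Part A doses and attends Week 12; nothing in the documents labels such a person as discontinued. The 30% rate is itself set against completion through Week 12.
- *About 15 weights are lost.* This applies about 30% to all 50 discontinuers. It needs every one of them to attend a further scheduled visit. Protocol 7.2 lists death, loss to follow-up and refusal of further follow-up, and the mapping of early discontinuation weights to Weeks 4, 8 or 12 is not stated.
- *Only sicker participants are affected, so the estimate is biased in a known direction.* Protocol 7.1 lists disease progression and hospitalization, but also allergic reaction and pregnancy. The direction cannot be derived.

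**Conclusion.** The inconsistency is real and small. At Weeks 4 and 8 the Censored set treats identical in-window weights differently according to whether the participant later counts as discontinued. About 29–31% of closing visits are affected with uniform visit days, and about 19–26% with visits clustered at the nominal day.

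The ceiling of about 10 weights assumes the 30% discontinuation rate, an even split of stopping over the three doses, full attendance and uniform days; the number in practice should be lower. The effect on the Week 12 estimate is indirect, through the MMRM, and likely to be small. This is worth correcting because the repair is cheap and the present rule discards valid observations, not because it threatens the trial's conclusion.

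**What to change.** Add to SAP section 4, in substance: for a participant who discontinues study intervention, the weight at the first scheduled Week 4, 8 or 12 visit after the last dose stays in the Censored set when it falls inside that visit's protocol window and no other intercurrent event came before it; observations after that visit are censored. Where this does not apply, last dose + 29 days remains.

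Two details are needed. Naming Weeks 4, 8 and 12 prevents the Week 5 or Week 10 weight from being taken as the first visit. The dose not given at the closing visit should count as the discontinuation itself, not as a separate missed dose. The SAP should also say how a participant with all three Part A doses is labelled.

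A flat last dose + 34 days is a weaker alternative: it exceeds the in-window maximum after dose 1 (31 days) and dose 3 (33 days), and so would admit some out-of-window weights.

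The cost is one sentence and a small change to the censoring program. No new data are needed, and the rule can be applied blinded. The downside is that a few weights taken 30 to 34 days after the last dose count as on treatment, as they already do for continuers. If the analysis sets are already locked, a sensitivity analysis that retains these weights would show whether they matter.

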5. GENERAL METHODOLOGY AND CONVENTIONS

5.1. Hypotheses and Decision Rules

The null hypothesis of no difference between ponsegromab and placebo will be tested for each primary, and selected secondary (physical activity, FAACT and CRCSD) and tertiary (PROMIS-fatigue, PROMIS-physical function, LSMI and survival status) endpoints. The alternative hypothesis is that ponsegromab is superior to placebo. The Type I error rate (α-level) used for the statistical inference will be 5% (1-sided). Each dose of ponsegromab will be compared separately with placebo. No adjustment for multiple comparisons will be made.

For all other endpoints, the results of any statistical analyses are for exploratory purposes only and there is no formal hypothesis testing.

5.2. General Methods

Unless otherwise stated, the main cohort and PK substudy will be reported together. Note that the separate presentations for the participants in the PK substudy may be reported in a supplemental CSR rather than the main CSR.

The analyses related to the primary, secondary and exploratory endpoints will be based on the appropriate population for analysis (see Section 4).

Unless otherwise stated, all summaries and plots will be presented by treatment group. The following treatment group labels (or similar) will be used:

- Placebo
- Ponsegromab 100mg
- Ponsegromab 200mg
- Ponsegromab 400mg

A 'Ponsegromab Combined' group will also be presented for safety summaries.

5.2.1. Summaries for Continuous Endpoints

Unless otherwise stated, continuous variables will be presented using summary statistics: number of observations, arithmetic mean, standard deviation (SD), median and Q1, Q3 and/or range (minimum and maximum) values. For endpoints to be analyzed on the natural log scale (log_e), the geometric mean and geometric coefficient of variation (CV) will additionally be calculated.

5.2.2. Summaries for Categorical Endpoints

Categorical variables will be presented using summary statistics: number of observations and percentages.

